5.8 Discontinuation of investigational product

Patients may be discontinued from investigational product in the following situations:

- Patient decision. The patient is at any time free to discontinue the investigational products, without prejudice to further treatment.
- Safety reasons (AE) as judged by the investigator, AstraZeneca and/or Bristol-Myers Squibb Pharmacovigilance.
- Severe non-compliance to the Clinical Study Protocol as judged by the investigator and/or AstraZeneca.
- Incorrect enrolment.
- Patient lost to follow-up (unable to reach the patient after three documented phone calls, fax, email, or attempts to contact him/her through patient locator agencies [if allowed per national regulation] and having sent one letter by registered/certified mail; all should be documented in the patient's medical records).

Study specific discontinuation criteria are listed below. The FPG, PPG and HbA_{1c} values will be measured at the central laboratory, whilst the patients will also determine their FPG daily using a Glucometer.

1. Use of (need for) additional anti-hyperglycaemic medication other than the investigational product for more than 7 consecutive days. Insulin for up to 7 days during hospitalisation will be allowed as long as the primary reason for hospitalisation is not management of the patient's glycaemic control.
2. Treatment with glucocorticoids equivalent to oral prednisolone >10 mg/day (two temporary periods of higher daily doses but no longer than 7 days each will be allowed).

3. Severe and/or frequent hypoglycaemic events, defined as ≥ 1 major event or recurring minor events and the possibility of down-titration of sulfonylurea and contributing factors (e.g., excessive physical activity) has been evaluated. Down-titration of sulfonylurea will be permitted once during the treatment period.
4. Patients whose individual treatment codes are broken by the investigator.
5. FPG > 15.0 mmol/L (>270 mg/dL) during the double-blind treatment period, between Visit 3 and Visit 6, confirmed at repeated measurement within 5 days (results from central laboratory). If self-monitored FPG > 15.0 mmol/L (>270 mg/dL) between Visit 3 and Visit 6, patient to repeat the self-monitoring of FPG within 2 days. If this second FPG is still >15.0 mmol/L (>270 mg/dL), the patient should contact the study centre and have this measure confirmed by central laboratory within 5 days for discontinuation.
6. FPG > 12.2 mmol/L (>220 mg/dL) during the double-blind treatment period, between Visit 6 and Visit 9, confirmed at repeated measurement within 5 days (results from central laboratory). If self-monitored FPG > 12.2 mmol/L (>220 mg/dL) between Visit 6 and Visit 9, to repeat the self-monitoring of FPG within 2 days. If this second FPG is still >12.2 mmol/L (>220 mg/dL), the patient should contact the study centre and have this measure confirmed by central laboratory within 5 days for discontinuation.
7. Calculated CrCl <60 ml/min or an increase in serum creatinine of ≥ 44.2 μ mol/L (≥ 0.5 mg/dL) above the baseline value confirmed at a repeated measurement within 1 week.
8. Serum total bilirubin >34 μ mol/L (>2 mg/dL) confirmed at a repeated measurement within 1 week.
9. Increase of ALT and/or AST >3 x ULN and increase of total bilirubin ≥ 2 x ULN confirmed at a repeated measurement within 1 week.
10. Increase of ALT or AST >5 x ULN confirmed at a repeated measurement within 1 week.
11. A temporary discontinuation of investigational product must occur when the patient receives intravascular administration of iodinated contrast agents. Since intravascular administration of iodinated contrast agents in radiologic studies can lead to renal failure, both metformin and investigational product should be temporarily stopped prior to, or at the time of the test and not re-instituted until at least 48 hours afterwards. Investigational product and metformin should also be temporarily stopped 48 hours before elective surgery with general anaesthesia and should not be resumed earlier than 48 hours afterwards.

5.8.1 .Procedures for discontinuation of a subject from investigational product

A patient that decides to discontinue the investigational product will always be asked about the reason(s) and the presence of any AEs. If possible, they will be seen and assessed by an

investigator(s). Adverse events will be followed up (See Sections 6.4.3 and 6.4.4); diary cards, glucometers, and the investigational product should be returned by the patient.

Randomised patients who do not complete the study should complete the procedures described for Visit 9 (End of Study Visit).

If a patient is withdrawn from the study, see Section 5.9.

5.9 Withdrawal from study

Patients are free to withdraw from study at any time (the investigational product and assessments), without prejudice to further treatment (withdrawal of consent). Such patients should always be asked about the reason(s) and the presence of any AEs. If possible, they will be seen and assessed by an investigator. Adverse events will be followed up (See Sections 6.4.3 and 6.4.4); diary cards, glucometers, and the investigational product should be returned by the patient.

A patient withdrawn from the study will not be replaced.

6. COLLECTION OF STUDY VARIABLES

6.1 Recording of data

The Rave Web Based Data Capture (WBDC) system will be used for data collection and query handling. The investigator will ensure that data are recorded on the eCRF as specified in the Clinical Study Protocol and in accordance with the instructions provided.

The investigator ensures the accuracy, completeness, and timeliness of the data recorded and of the provision of answers to data queries according to the Clinical Study Agreement.

Data must be entered into the WBDC system at the study centre within 72 hours after the scheduled visit (except for SAEs that should be entered within 1 calendar day). Trained study personnel will be responsible for entering data into the WBDC system according to the Instructions for the investigator including the data entry instructions. Data includes observations, tests and assessments specified in the Clinical Study Protocol.

When data have been entered, reviewed, edited and source data verification has been performed by an AstraZeneca representative, the data will be frozen to prevent further editing. The Principal Investigator is responsible for signing the eCRF and this can be delegated to a trained investigator. The eCRF is signed electronically as per the eCRF instructions. A copy of the eCRF data will be archived at the study centre.

Data verification and validation will be performed. The Investigator should answer any external queries raised by AstraZeneca in a timely manner, and query resolutions will be saved in the central database.

Health-related quality of life (EQ-5D) questionnaire will be completed in paper. Data will be entered on the eCRF by trained study personnel.

6.2 Data collection and enrolment

The following data will be collected and recorded in the appropriate sections of the eCRF (refer to the Study Plan, Section 3.1).

- Date of signed informed consent
- Inclusion and exclusion criteria
- Demography: Date of birth, gender and ethnicity
- Timing of laboratory assessments
- Pregnancy test
- Medical history
- Physical examination (see Section 6.4.6) including vital signs, height, weight and waist circumference
- A 12-lead ECG, see Section 6.4.7
- Prior and concomitant medication
- Data from patient reported outcome questionnaires

6.2.1 Follow-up procedures

Randomised patients who do not complete the study should complete the procedures described for Visit 9 (End of Study Visit).

6.3 Efficacy

Baseline is defined as the last non-missing value before the first dose of double-blind treatment on Week 1 (Day 1).

Self-monitoring of plasma glucose should be done in order to reduce the risk of prolonged periods of undetected hyperglycaemia or to confirm hypoglycaemia. Patients will be asked to do self-monitoring of plasma glucose using glucometers provided by AstraZeneca. The patients will receive training on the use of the glucometer, according to the manufacturer's instruction.

6.3.1 Efficacy variables

The laboratory variables that will be measured to assess efficacy and the visits these will be measured are presented in Table 2. These variables will be assessed at the central laboratory.

For information on methods of collection, assessment, labelling, storage and shipment of samples, see the Laboratory Manual.

Table 2 Efficacy laboratory variables

Visit number	1	2	3	4	5	6	7	8	9
Study week	-2	-1	1	4	8	12	16	20	24
Study Day	-14	-7	1	28	56	84	112	140	168
HbA1c	X		X	X	X	X	X	X	X
FPGb			X	X	X	X	X	X	X
PPGa			X						X
Insulinb			X						X
C-peptide			X						X
Glucagon			X						X

FPG: Fasting plasma glucose, PPG: Postprandial glucose.

a. Measured 2 hours after breakfast; b. Fasting

Patients should be instructed to abstain from all food and beverages for 10 hours prior to each clinical visit; however, drinking water is allowed. In the morning prior to each visit, acceptable concomitant medications can be taken, but with water only.

The patient should not take any investigational product in the morning before the scheduled visit, but after the relevant laboratory specimens have been collected. The investigational products will be taken at breakfast which will be provided at the study centres during the scheduled visits. Laboratory samples for the PPG will be collected after the patient has had breakfast.

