Figure 1 Study flow chart for screening, enrolment period and double-blind treatment period

MTD: Maximum tolerated dose

* Minimum dose of metformin for enrolment = 1500 mg

** Minimum dose for sulfonylurea for enrolment is 50% of the maximum recommended dose:

Note: Patients will continue taking metformin and sulfonylurea at doses ascertained at enrolment, during the double-blind treatment period. Saxagliptin and Placebo will be administered as add-on therapy.

In this study, each patient will be enrolled on a stable combined dose of metformin XR or IR (MTD, with minimum dose for enrolment being 1500mg) and sulfonylurea (MTD, with minimum dose for enrolment being $\geq 50\%$ of the maximum recommended dose) for at least 8 weeks prior to Visit 1.

.Note: Patients must be on MTD of metformin IR or XR (minimum dose for enrolment being 1500 mg) and on MTD of sulfonylurea (minimum dose for enrolment being 50% of maximum recommended dose).

Following Informed Consent, patients will be pre-screened for HbA_{1c} – at Visit 1, within 14 days prior to randomisation. Patients whose HbA_{1c} is $\geq 7\%$ and $\leq 10\%$, as confirmed by central laboratory, will undertake safety and other assessments at Visit 2 (Day -7) to confirm remaining eligibility criteria. Patients who meet all of the inclusion criteria and none of the exclusion criteria will be randomised at Visit 3 and will commence the 24-week double-blind treatment period.

During the 24-week double-blind treatment period of the study, patients will still receive metformin and sulfonylurea at the dose ascertained during enrolment. In addition, patients will be randomised, at Visit 3, to receive the following:

- Double-blind saxagliptin 5 mg, orally, od or
- Double-blind matching placebo orally, od.

The study will consist of two periods:

Screening/enrolment period

Patients with type 2 diabetes who have inadequate glycaemic control (HbA_{1c} $\geq 7\%$ and $\leq 10\%$) and are currently on a stable combined dose of metformin XR or IR (MTD) and sulfonylurea (MTD) for at least 8 weeks prior to Visit 1 are eligible for enrolment. Blood samples for assessment of inclusion and exclusion criteria will be taken at Visit 1 and Visit 2 and assessed at the central laboratory before randomisation

Randomisation and double-blind treatment period

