Patients with HbA_{1c} $\geq 7\%$ and $\leq 10\%$, as confirmed by the central laboratory and who meet all the inclusion and none of the exclusion criteria, will be randomised (1:1) at Visit 3 to one of the following two treatment groups:

- Double-blind saxagliptin (5 mg od) or
- Double-blind matching placebo

At Visit 3, either one tablet of double-blind 5 mg saxagliptin or a matching placebo tablet will be added to the metformin and sulfonylurea (same dose as being used at Visit 1) treatment.

The patient will return every 4 weeks (Visit 4 to Visit 9), and blood glucose measurements made by the patient since the last visit, the gastrointestinal tolerability and the FPG value (performed at the central laboratory) will be assessed.

Matching placebo tablets for saxagliptin will be given as appropriate for the 24-week double-blind treatment period of the study.

Fasting plasma glucose will be measured at the central laboratory every 4 weeks during the double-blind treatment period. The metformin and sulfonylurea doses must remain constant during the 24-week double-blind treatment period (Visit 3 to Visit 9) to ensure a steady state effect of the HbA_{1c} which is the primary endpoint of the study. Sulfonylurea may be down-titrated once in the case of major hypoglycaemic event or recurring minor hypoglycaemic events. (Refer to Section 5.8). Titration (up or down) of study medication during the treatment period (Visit 3 to Visit 9) is prohibited. Blood samples for the assessment of the glycaemic parameters (based on results from the central laboratory) will be taken at each visit to determine if criteria for discontinuation of the investigational product are met. The patients will be instructed to monitor their fasting blood glucose levels at least every other day and to register the values associated with hypoglycaemic events into their patient diary.

During the double-blind treatment period, dietary and lifestyle modification will be re-enforced.

Finally, randomised patients who do not complete the study should complete the procedures described for Visit 9 (End of Study Visit).

Table 1 Study plan for screening, enrolment period and double-blind treatment period

Study period	Screening / Enrolment		Double-blind treatment period						
	Enrolment	Screening	Randomisation						
Visit label	1	2	3	4	5	6	7	8	9a
Visit number	1	2	3	4	5	6	7	8	9a
Study Week	-2	-1	1	4	8	12	16	20	24
Study Day	-14 to -10	-9 to -5	0	28	56	84	112	140	168

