5.5.2 Doses and treatment regimens

During the screening period (Visit 1 to Visit 3) each patient will continue receiving a stable combined dose of metformin XR or IR and sulfonylurea at the dose ascertained during enrolment (Visit 1).

Patients will be randomised at Visit 3 to one of the following two treatment groups:

- Double-blind saxagliptin (5 mg od) as add-on therapy to metformin plus sulfonylurea (same dose as being used at Visit 1)

or

- Double-blind placebo matching saxagliptin as add-on therapy to metformin plus sulfonylurea (same dose as being used at Visit 1)

After the randomisation visit (Visit 3), either a double-blind tablet of saxagliptin 5 mg or placebo will be administered in the morning as add-on therapy to the metformin and sulfonylurea.

The patients will return every 4 weeks (Visits 4 to 9) for evaluation of the blood glucose measurements made by him/her since the last visit, the gastrointestinal tolerability and the FPG value (performed at the central laboratory at each visit).

The investigational product or matching placebo as well as metformin and sulfonylurea will be taken orally and together with meals, at approximately the same time of the day during the study period. The doses to be taken in the morning should not be taken before the scheduled visit but after the relevant laboratory specimens have been collected. The investigational products plus metformin and sulfonylurea will be taken at breakfast (standardised breakfast packs provided) which will be provided at the study centres during the scheduled visits. Patients should be instructed to abstain from all food and beverages for 10 hours prior to each scheduled visit; however, drinking water is allowed. In the morning prior to each scheduled visit, acceptable concomitant medications can be taken, but with water only.

The following investigational products and doses will be used during the double-blind treatment period:

- Double-blind saxagliptin oral tablets, 5 mg, od for the 24-week double-blind treatment period
- Matching oral placebo tablets for saxagliptin, 5 mg, od for the 24-week double-blind treatment period

Visit ID	No. of bottles to dispense of saxagliptin 5 mg or matching placebo^a
Visit 1	N/A
Visit 2	N/A
Visit 3	1 bottle
Visit 4	1 bottle
Visit 5	1 bottle
Visit 6	1 bottle
Visit 7	1 bottle
Visit 8	1 bottle
Visit 9	N/A

^a Each bottle contains 35 tablets.

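### The protocol gives conflicting instructions on whether the first double-blind tablet comes before or after the Visit 3 two-hour PPG sample, the only possible PPG baseline

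*Protocol*

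**What the plan says.** Change in PPG from Baseline to Week 24/Endpoint is a secondary efficacy objective (Protocol 2.2). Table 2 schedules PPG at Visits 3 and 9 only, two hours after breakfast, and Table 4 budgets two PPG samples per patient.

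Text that puts the tablet before the sample:
- Section 6.3.1: "The investigational products will be taken at breakfast which will be provided at the study centres during the scheduled visits". The next sentence reads: "Laboratory samples for the PPG will be collected after the patient has had breakfast".
- Section 5.5.2 repeats the rule: "The investigational products plus metformin and sulfonylurea will be taken at breakfast".
- Section 3.1 says that eligible patients "will be randomised at Visit 3 and will commence the 24-week double-blind treatment period". It has the study tablet added to the background drugs at Visit 3, and it counts Visit 3 as inside the treatment period: "during the 24-week double-blind treatment period (Visit 3 to Visit 9". The first bottle is dispensed at that visit (table in 5.5.2).

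Text that points the other way:
- Section 5.5.2: "After the randomisation visit (Visit 3), either a double-blind tablet of saxagliptin 5 mg or placebo will be administered in the morning".
- Section 6.3.1 says the patient "should not take any investigational product in the morning before the scheduled visit, but after the relevant laboratory specimens have been collected", with similar wording in 5.5.2. Neither place says whether the two-hour PPG counts among those specimens.

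Sections 6.3 and 11.1.1 define baseline as the latest available measurement preceding the first double-blind dose, which they place on Day 1 of Week 1. Section 12.2.1 analyses continuous secondary variables by ANCOVA with the baseline value as covariate and describes the secondary analyses as exploratory.

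**The concern.** Two centres can follow this protocol in good faith and do opposite things at Visit 3. One gives the first tablet with the clinic breakfast and draws PPG two hours later. The other holds the tablet until the sample is drawn, or until the next morning. No PPG is taken before Visit 3, so in the first centre no value meets the protocol's definition of a PPG baseline.

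Two consequences are possible for those patients. If the definition is followed, they have no PPG change score and drop out of that ANCOVA. They stay in the Full Analysis set, because 12.1.4 asks for a baseline in only one efficacy parameter, and carrying observations forward repairs only post-baseline gaps. If the Visit 3 value is used anyway, the covariate may already carry part of the drug effect in the saxagliptin arm, and adjusting for it would shrink the estimated difference.

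**Working it through.** **Order of events.** Set the clinic breakfast at time 0.
1. Under the breakfast rule (5.5.2, 6.3.1) the tablet is taken at time 0.
2. PPG is drawn at time 0 + 2 h (Table 2, footnote a).
3. So the tablet precedes the sample by about 2 h. A tablet taken at breakfast cannot also follow a sample drawn two hours after breakfast, so the two sets of instructions cannot both hold at Visit 3.

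**Can the day labels decide?** Sections 6.3 and 11.1.1 put the first dose on Day 1.

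| Source | Label for Visit 3 or randomisation | Implied first dose |
|---|---|---|
| Table 1 | Day 0 | the day after Visit 3 |
| Tables 2 and 3 | Day 1 | the day of Visit 3 |
| Section 12.1.2 | Day 1 | the day of randomisation |

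They disagree. Even a same-day label would not give the order within the morning.

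**The plan's own figures.** The protocol has none for PPG. The HbA1c calculation in 12.3 (difference 0.40, SD 1.1, two-sided 0.05, 80% power) reproduces: 119 per group against the stated 120, and t-test power of 80.1% with 120 per group. It is unaffected by this point.

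**Illustrations only.** Every input below is an assumption. Let p be the share of patients given the tablet before the Visit 3 sample, b the ANCOVA slope on baseline, and f the share of the Week 24 PPG effect already present two hours after the first tablet.

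*Baseline definition followed.* Patients left = 240(1 − p); SE multiplier = 1/√(1 − p). The power column borrows the HbA1c standardised effect, 0.40/1.1 = 0.364, because none is given for PPG.

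| p | patients | SE multiplier | power |
|---|---|---|---|
| 0 | 240 | 1.00 | 80% |
| 0.25 | 180 | 1.15 | 68% |
| 0.50 | 120 | 1.41 | 51% |
| 0.75 | 60 | 2.00 | 28% |

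This costs precision but adds no bias: allocation is blinded, so the order of tablet and sample cannot depend on the arm. At p = 1 no PPG change analysis remains.

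*Post-dose value used as baseline.* Share of the true difference retained = 1 − b·f·p.
- f = 0 or p = 0: 100%.
- b = 0.5, p = 0.5: f = 0.25 gives 1 − 0.0625 = 94%; f = 0.5 gives 1 − 0.125 = 88%.
- b = 0.5, p = 1: f = 0.25 gives 1 − 0.125 = 88%; f = 0.5 gives 1 − 0.25 = 75%.
- p = 1, f = 0.5: b = 0.3 gives 85%; b = 0.7 gives 65%.

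Section 1.1.3 says peak plasma concentration is usually reached within 2 hours of dosing, so some effect at the sampling time is possible. It gives no glucose effect at that time, so f is unknown.

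**The case against.** The best defence is that the protocol does contain a sentence specific to the first dose, the one in 5.5.2 placing it after Visit 3, and that a specific instruction governs a general one. The breakfast rule also cannot be literal for every scheduled visit, since no study product exists at Visits 1 and 2. The sentence before it, about not dosing before coming to the centre, can bind only patients who already hold tablets, that is from Visit 4 on. Table 1 measures its visit windows from Visit 3 as Day 0, which fits a first dose the next morning. A baseline defined as pre-dose suggests that the Visit 3 PPG was meant to be among the specimens drawn first. Finally, 6.3.1 delegates sample procedures: "For information on methods of collection, assessment, labelling, storage and shipment of samples, see the Laboratory Manual".

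Much of this stands as evidence of what may have been intended, and some or all centres may have drawn the sample first. It does not settle the text. Section 3.1 adds the tablet at Visit 3, and section 12.1.2 puts randomisation on the same Day 1 as the first dose. If the specimens rule covered PPG, it would equally push the Visit 9 tablet behind the Visit 9 sample, against the breakfast rule. The Laboratory Manual is not shown and may set an order; what 6.3.1 refers to it is sample handling, while dosing is governed by the protocol.

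The objection that the loss figures are invented stands in full: nothing in the protocol supports any particular p, b or f, and it claims no power for PPG.

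**Conclusion.** The instructions conflict, and the conflict falls on the one sample that has no substitute under the protocol's definition of baseline. The point is worth correcting as a cheap improvement in wording. HbA1c, fasting glucose and the sample size are untouched; the only endpoint affected is a secondary one declared exploratory.

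Three stronger conclusions are tempting but not supported.
- A reader might infer that the baseline PPG is definitely post-dose. The 5.5.2 sentence and Table 1 allow the opposite order.
- A reader might take the power or attenuation figures as the expected loss. They rest wholly on assumed inputs, and the harm is nil if every centre draws the sample first; the bias is nil if the first dose has no two-hour effect.
- A reader might conclude that the PPG comparison would be lost beyond repair. A missed pre-dose PPG cannot be recovered, but Week 24 PPG could still be compared with pre-dose fasting glucose and HbA1c, both scheduled at Visit 3, as covariates, at some cost in precision.

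**What to change.** State in 5.5.2 and 6.3.1 that at Visit 3 metformin and sulfonylurea are taken with the clinic breakfast and the first double-blind tablet only after the two-hour PPG sample, or the next morning. State also that at Visit 9 the double-blind tablet is taken with breakfast, before the PPG sample. Align the Visit 3 wording in 3.1, and use one day label for Visit 3 in Tables 1 to 3 and in 6.3, 11.1.1 and 12.1.2.

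The cost is a first dose delayed by about two hours to one day. No visit, sample or breakfast is added. Supply is sufficient: at the widest windows the Visit 8 bottle must last from Day 137 to Day 171 inclusive, 171 − 137 + 1 = 35 tablets, and it holds 35. A fallback covariate analysis for any post-tablet Visit 3 samples is optional and belongs in the SAP.
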